8.1.2 Secondary Objectives & Hypotheses

Any patient who receives at least one dose of pembrolizumab will be included in efficacy analyses.

(1) Objective: To describe the overall response rate (ORR) to pembrolizumab in patients failing to respond to or relapsing after anti-CD19 chimeric antigen receptor modified T cell therapy for relapsed or refractory CD19+ lymphomas.

Methodology: For efficacy, a sample size of 12 patients achieves an 80% power to detect a difference (P1 0.35 – P0 0.05) of 0.30 using a one-sided binomial test for ORR. The target of significance level is 0.05. This response rate prediction of 35% is based on the reported 28% response rate reported for nivolumab, another anti-PD1 blocking antibody, in patients with B cell lymphoma. This also assumes that a 5% response rate would be seen if pembrolizumab does not have efficacy in this population. If the response rate is 3 or more, the hypothesis that the ORR is ≤ 0.05 is rejected. If the number of responses is 2 or less, the hypothesis that ORR is ≥ 0.35 .

Hypothesis: The response rate after pembrolizumab will be 3 or more, allowing us to reject the null hypothesis that pembrolizumab after CTL019/CTL119 has an ORR ≤ 0.05

(2) Objective: To describe the clinical efficacy of pembrolizumab, including progression-free survival, disease-free survival, event-free survival, response duration, and overall survival (Cheson, 2007) in patients failing to respond to or relapsing after anti-CD19 chimeric antigen receptor modified T cell therapy for relapsed or refractory CD19+ lymphomas. Efficacy comparisons will be made with both most recent prior therapy as well as with CTL019/CTL119.

Methodology: Kaplan Meier survival analysis will be used to estimate progression-free survival, event-free survival, response duration, and overall survival. For patients with initial responses to both CTL 019 and pembrolizumab, progression-free survival, event-free survival, and response duration, patients' response to CTL 019 therapy will be compared to their response to pembrolizumab using the log-rank test, with $p \leq 0.05$ considered statistically significant.

Hypothesis: Pembrolizumab will enhance the efficacy of CTL019/CTL119 in patients failing to respond to or relapsing after chimeric antigen receptor modified T cell therapy for relapsed or refractory CD19+ lymphomas.

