1.0 TRIAL SUMMARY

Title	Phase I/II study of pembrolizumab in patients failing to respond to or relapsing after anti-CD19 chimeric antigen receptor modified T cell therapy for relapsed or refractory CD19+ lymphomas
Abbreviated Title	Pembrolizumab after CTL019/CTL119 for relapsed/refractory CD19+ lymphomas
Trial Phase	Phase I / II
Clinical Indication	Relapsed / refractory CD19+ B cell lymphomas after CTL019/CTL119
Trial Type	Investigator-initiated
Type of control	None. Enrollment will be offered to subjects with an unmet medical need, which is no available effective, standard therapy for relapsed / refractory CD19+ lymphomas
Route of administration	Intravenous
Trial drug, dose, route, regimen	Pembrolizumab (Keytruda [®]) 200mg fixed dose IV every 3 weeks
Trial Blinding	None
Treatment Groups	Single group
Number of trial subjects	12 evaluable subjects
Estimated enrollment period	12 months (approximately January 2016-January 2017)
Estimated duration of trial	36 months (approximately January 2016-January 2019)
Duration of Participation	24 months (12 months treatment + 12 months follow-up)
Objectives	
Primary Endpoints:
 
 1. Determine safety of pembrolizumab after CTL019/CTL119. This endpoint will be met if $\leq 30\%$ of patients develop toxicity resulting discontinuation of pembrolizumab. 2. Determine efficacy of pembrolizumab after CTL019/CTL119. This endpoint will be met if the ORR at 3 months is $\geq 35\%$.
Statistical methodology	
Primary Endpoints:
 
 1. Safety endpoint will be assessed using a Bayesian monitoring rule to ensure probability of a patient developing toxicity resulting in discontinuation of pembrolizumab $\leq 30\%$ 
Secondary Endpoints:
 
 1. ORR will be assessed using a one-sided binomial test 2. PFS, EFS, RD, and OS will be assessed using Kaplan Maier survival analysis. PFS after pembrolizumab will be compared to PFS after CTL019/CTL119 using a log rank test.

This document is confidential and the property of the University of Pennsylvania. No part of it may be transmitted, reproduced, published, or used by other persons without prior written authorization from the regulatory sponsor.

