4.2 Rationale

4.2.1 Rationale for the Trial and Selected Subject Population

We are currently conducting a phase IIA clinical trial of redirected autologous T cells, engineered to contain anti-CD19 attached to 4-1BB and TCR ζ signaling domains, in patients with chemotherapy relapsed or refractory CD19+ lymphomas (NCT02030834). Briefly, autologous T cells collected from eligible patients with diffuse large B cell, follicular, and mantle cell lymphomas are transduced using a lentiviral vector to express a chimeric antigen receptor comprised of an extracellular single chain antibody (scFv) with specificity for CD19 in tandem with an intracellular signaling domain comprised of 4-1BB and TCR ζ signaling molecules. The transduced T cells have specificity for cells expressing CD19, a molecule that is restricted in expression to the surface of B cell lymphoma cells as well as normal B cells. Therapy with anti-CD19 chimeric antigen receptor modified T cells has shown efficacy in chronic lymphocytic and acute lymphoblastic leukemias (Porter, 2011; Grupp, 2013; Maude, 2014). On our lymphoma trial, to date, 7 of 7 evaluable patients with relapsed or refractory follicular lymphoma have responded to anti-CD19 chimeric antigen receptor modified T cell therapy (100% response rate and at a median follow-up of 290 days, only one patient has had progression of disease [*[name], preliminary data*]), while only 6 of 12 evaluable patients with relapsed or refractory diffuse large B cell lymphoma have responded to therapy (50% response rate; 5 of 6 patients have ongoing complete responses at median follow-up of 274 days [*[name], preliminary data*]). We have preliminary evidence that the PD-1 receptor-ligand pathway may have a role in patients failing to respond to chimeric antigen receptor

This document is confidential and the property of the University of Pennsylvania. No part of it may be transmitted, reproduced, published, or used by other persons without prior written authorization from the regulatory sponsor.

modified T cell therapy, since we have observed increased expression of PD-1 on CTL019/CTL119 with decreased TNF- α and IFN- γ levels in the setting of progressive disease. This has also been demonstrated in a laboratory model of CAR T cells in combination with PD-1 blockade (John, 2013).

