5.1.3 Subject Exclusion Criteria

The subject must be excluded from participating in the trial if the subject:

1. Is currently participating and receiving study therapy or has participated in a study of an investigational agent and received study therapy or used an investigational device within 4 weeks of the first dose of treatment. An exception will be made for patients who have received CTL019/CTL119 on experimental protocol; these patients will be eligible to enroll once progression of disease or failure to respond is documented by clinical or radiologic assessment.
2. Patient has received intervening therapy for lymphoma after CTL019/CTL119 infusion.
3. Has active cytokine release syndrome from CTL019/CTL119 infusion.
4. Has a known history of active TB (Bacillus Tuberculosis).
5. Hypersensitivity to pembrolizumab or any of its excipients.
6. Has had a prior anti-cancer monoclonal antibody (mAb) within 4 weeks prior to study Day 1 or who has not recovered (i.e., \leq Grade 1 or at baseline) from adverse events due to agents administered more than 4 weeks earlier. Toxicities that are disease related will not exclude patients.
7. Has had prior chemotherapy, targeted small molecule therapy, or radiation therapy within 2 weeks prior to study Day 1 or who has not recovered (i.e., \leq Grade 1 or at baseline) from adverse events due to a previously administered agent.
 - Note: Subjects with \leq Grade 2 neuropathy are an exception to this criterion and may qualify for the study.
 - Note: If subject received major surgery, they must have recovered adequately from the toxicity and/or complications from the intervention in the opinion of the Principal Investigator prior to starting therapy.
8. Has a known additional malignancy that is progressing or requires active treatment. Exceptions include basal cell carcinoma of the skin or squamous cell carcinoma of the skin that has undergone potentially curative therapy or in situ cervical cancer.
9. Has known active central nervous system (CNS) metastases and/or carcinomatous meningitis. Subjects with previously treated brain metastases may participate provided

This document is confidential and the property of the University of Pennsylvania. No part of it may be transmitted, reproduced, published, or used by other persons without prior written authorization from the regulatory sponsor.

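### Section 8.1.2(2) tests PFS and EFS against CTL019/CTL119 only in patients who responded to both therapies: about 1 to 3 patients, and a restriction that Section 1 does not mention

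*Combined protocol and SAP*

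**What the plan says.** Three statements bear on who enters this comparison.

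- Section 1, statistical methodology: "PFS after pembrolizumab will be compared to PFS after CTL019/CTL119 using a log rank test". No population is named.
- Section 8.1.2, first sentence: "Any patient who receives at least one dose of pembrolizumab will be included in efficacy analyses".
- Section 8.1.2, objective (2), methodology: "For patients with initial responses to both CTL 019 and pembrolizumab, progression-free survival, event-free survival, and response duration" are compared between the two therapies by a log-rank test, with p ≤ 0.05 taken as significant. Sidedness is not stated.

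The objective and hypothesis cover both patients who did not respond to CTL019/CTL119 and patients who relapsed after it. The objective adds: "Efficacy comparisons will be made with both most recent prior therapy as well as with CTL019/CTL119". Exclusion criterion 2 in Section 5.1.3 rules out a patient on this ground: "Patient has received intervening therapy for lymphoma after CTL019/CTL119 infusion".

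The plan gives no sample size, event count or power for this comparison, and it does not say how many dual responders (patients who responded to both therapies) it expects.

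**The concern.** A reader of Section 1 expects a comparison in the treated population. A reader of the 8.1.2(2) methodology finds a test in a subset defined by response to both therapies. Nothing reconciles the two, so the choice of set could be made after the data are seen.

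The subset is also awkward in itself. Restricting response duration to responders is natural, because only responders have one. PFS and EFS are different: response to pembrolizumab is part of the outcome being assessed, and those who do not respond, usually the earliest to progress, leave the curve. Requiring a response to CTL019/CTL119 removes the primary failures, who are half of the population that the objective describes and, on the protocol's own background data, most of it. What remains may be too few patients for the test to be able to reach its significance level.

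Two wording points sit in the same objective. The methodology writes CTL 019 where the objective writes CTL019/CTL119. And because exclusion 2 bars lymphoma therapy after the infusion, the most recent prior therapy of an eligible patient is CTL019/CTL119 itself unless the term is defined otherwise.

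**Working it through.** **Inputs**

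- Planned size: "12 evaluable subjects" (Section 1).
- Pembrolizumab ORR: 0.35, the design alternative in Section 8.1.2; 0.28, the nivolumab rate cited there, as sensitivity.
- Parent-trial counts in Section 4.2.1. Follicular: 7 of 7 responded and 1 has progressed. Diffuse large B-cell: "only 6 of 12 evaluable patients with relapsed or refractory diffuse large B cell lymphoma have responded to therapy", and 5 of those 6 have ongoing complete responses.

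**The plan's own figure.** Section 8.1.2 states that "a sample size of 12 patients achieves an 80% power to detect a difference (P1 0.35 – P0 0.05) of 0.30", rejecting at 3 or more responses. The exact binomial gives P(X ≥ 3 | 12, 0.05) = 0.0196 and P(X ≥ 3 | 12, 0.35) = 0.849. With 11 patients the power is 0.79987, so 12 is the smallest size that reaches 80%. The figure reproduces if 80% is read as a minimum. It concerns ORR only.

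**Share of prior responders among CTL019 failures.** Non-responders: 12 − 6 = 6. Relapsed responders: 1 follicular, plus 6 − 5 = 1 diffuse large B-cell patient no longer in complete response, assumed relapsed. The pool is 6 + 1 + 1 = 8, so the share is f = 2/8 = 0.25.

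**Size of the dual-responder set.** With independent responses, the count is Binomial(12, f × ORR). At the base case, 0.25 × 0.35 = 0.0875 and the mean is 12 × 0.0875 = 1.05. P(0) = 0.33.

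| f | ORR | Mean | P(≤1) | P(≥2) | P(≥3) |
|---|---|---|---|---|---|
| 0.25 | 0.28 | 0.84 | 0.80 | 0.20 | 0.05 |
| 0.25 | 0.35 | 1.05 | 0.72 | 0.28 | 0.08 |
| 0.40 | 0.35 | 1.68 | 0.48 | 0.52 | 0.23 |
| 0.50 | 0.35 | 2.10 | 0.35 | 0.65 | 0.35 |
| 13/19 | 0.35 | 2.87 | 0.18 | 0.82 | 0.58 |
| 1.00 | 0.35 | 4.20 | 0.04 | 0.96 | 0.85 |

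The 13/19 row supposes that all 7 + 6 = 13 responders later relapse and join the 6 non-responders. The last row, with every enrolled patient a prior responder, is the ceiling at that ORR.

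**Smallest p-value the test can give.** Take k patients per curve, no censoring, and every time on one curve shorter than every time on the other. Chi-square = (O − E)²/V, summed over the first k event times.

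- k = 1: E = 1/2, V = 1/4. Chi-square = 0.5²/0.25 = 1.00, two-sided p = 0.317, one-sided 0.159.
- k = 2: E = 1/2 + 1/3 = 0.833, V = 1/4 + 2/9 = 0.472. Chi-square = 1.167²/0.472 = 2.88, two-sided p = 0.090, one-sided 0.045.
- k = 3: E = 1/2 + 2/5 + 1/4 = 1.15, V = 0.25 + 0.24 + 0.1875 = 0.6775. Chi-square = 1.85²/0.6775 = 5.05, two-sided p = 0.025.

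So a two-sided test needs at least 3 dual responders and a one-sided test at least 2. These are large-sample approximations. The smallest two-sided permutation p for two independent groups of 3 is 2/20 = 0.10, so the thresholds are, if anything, generous.

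**The case against.** Section 1 is a one-line synopsis that omits a restriction, which is weaker than stating a rival population. The opening sentence of 8.1.2 can be read as a default that a named subset overrides. This stands in part: a reader might infer that Section 1 prescribes a test in exactly 12 patients, but it names no population. Section 5.8 also allows replacement of some early withdrawals while keeping them in the efficacy analyses, so that set may exceed 12. The sections still need aligning, because nothing says that the subset overrides the default.

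A reader might also infer that the restriction tilts the comparison towards pembrolizumab. The documents do not support a net direction. Pembrolizumab non-responders leave one curve, but CTL019/CTL119 non-responders leave the other.

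Moving to all dosed patients has a bias of its own. Eligibility requires failure of CTL019/CTL119, so essentially every time on that curve ends in an event, and most patients in the Section 4.2.1 pool are primary non-responders. This objection stands in full. It is why the all-dosed comparison should carry no significance claim.

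The estimate of about one is fragile. It comes from an early snapshot at median follow-up of 274 to 290 days, with one relapse assumed and no mantle cell counts although mantle cell lymphoma is eligible. Later relapses would raise the share. The need for 3 patients holds only for a two-sided test; the plan states no sidedness, and its hypothesis is directional.

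Finally, CTL 019 is plausibly shorthand, so reading it as excluding CTL119 recipients would be strained. The most recent prior therapy may well mean the one before CTL019/CTL119. Both call only for clearer wording.

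**Conclusion.** The concern holds in a limited form. The population of this secondary comparison is not stated consistently. For PFS and EFS, the 8.1.2(2) restriction selects on outcome and leaves out the CTL019/CTL119 non-responders whom the objective and hypothesis include. These conclusions follow from the text and need no assumption about numbers.

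The size does need assumptions: enrolment like the Section 4.2.1 pool, independent responses and an ORR of 0.35. On these, about 1 dual responder is expected among 12, and about 1 to 3 across plausible prior-responder shares. At the base case the chance of having enough patients for p ≤ 0.05 to be attainable at all is 8% two-sided or 28% one-sided. If half of those enrolled had responded to CTL019/CTL119, it is 35% or 65%.

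The primary endpoint and the sample size do not depend on this comparison. It should be corrected because it decides what can be claimed under objective (2).

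**What to change.** - In 8.1.2(2), remove the p ≤ 0.05 log-rank test in dual responders and list their paired response durations instead.
- Present PFS and EFS after CTL019/CTL119 and after pembrolizumab for all dosed patients, as Kaplan-Meier curves or a paired listing, with no significance claim. State that every enrolled patient has by eligibility already failed CTL019/CTL119, so that curve is selected on failure.
- Align the statistical methodology entry in Section 1 with this.
- Write CTL019/CTL119 throughout. Define the most recent prior therapy as the last therapy before CTL019/CTL119, or delete that comparison.

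This changes wording only and does not affect the sample size. The cost is the loss of a formal p-value for an unpowered secondary comparison. If the earlier-therapy comparison is kept, the plan should confirm that response and progression dates for that therapy are collected.

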3.2 Secondary Objectives & Hypotheses

(1) Objective: To describe the overall response rate (ORR) at 3 months to pembrolizumab in patients failing to respond to or relapsing after CTL019/CTL119 for relapsed or refractory CD19+ lymphomas. To describe the clinical efficacy of pembrolizumab, including progression-free survival, disease-free survival, event-free survival, response duration, and overall survival (Cheson, 2007) in patients failing to respond to or

This document is confidential and the property of the University of Pennsylvania. No part of it may be transmitted, reproduced, published, or used by other persons without prior written authorization from the regulatory sponsor.

relapsing after CTL019/CTL119. Efficacy comparisons will be made for ORR between CTL019/CTL119 and pembrolizumab.

Hypothesis: Pembrolizumab will enhance the efficacy of CTL019/CTL119 in patients failing to respond to or relapsing after CTL019/CTL119 for relapsed or refractory CD19+ lymphomas (John, 2013).

- (2) **Objective:** To describe the immunophenotypic and cytokine profiles of chimeric antigen receptor modified T cells in these patients before and after therapy with pembrolizumab

Hypothesis: Immunophenotypic profiles of tumor cells and chimeric antigen receptor modified T cells obtained pre and post pembrolizumab therapy will identify patients for whom pembrolizumab will enhance efficacy.

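### Three overlapping log-rank comparisons with CTL019 each carry a p≤0.05 claim for one enhancement hypothesis, with no deciding contrast, and Sections 1 and 3.2 name different comparisons

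*Combined protocol and SAP*

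**What the plan says.** Section 8.1.2, objective (2), names three endpoints for comparison with CTL019: PFS, event-free survival (EFS) and response duration. After PFS the sentence reads "event-free survival, and response duration, patients' response to CTL 019 therapy will be compared to their response to pembrolizumab using the log-rank test". The population is limited by the words "For patients with initial responses to both CTL 019 and pembrolizumab". The threshold attached to every one of these tests is "with $p \leq 0.05$ considered statistically significant". The hypothesis attached to the objective is "Pembrolizumab will enhance the efficacy of CTL019/CTL119 in patients failing to respond to or relapsing after chimeric antigen receptor modified T cell therapy".

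The same objective adds a second comparator: "Efficacy comparisons will be made with both most recent prior therapy as well as with CTL019/CTL119". The methodology gives no test for comparison with the most recent prior therapy.

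Two other sections describe the comparison differently:
- Section 1 (Statistical methodology): "PFS after pembrolizumab will be compared to PFS after CTL019/CTL119 using a log rank test". No other endpoint is tested against CTL019/CTL119 and no population is stated.
- Section 3.2: "Efficacy comparisons will be made for ORR between CTL019/CTL119 and pembrolizumab". Section 8 gives no test for this. The one-sided binomial test in 8.1.2(1) is against a fixed 5% rate, not against CTL019/CTL119.

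Exclusion 2 in Section 5.1.3 reads "Patient has received intervening therapy for lymphoma after CTL019/CTL119 infusion".

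**The concern.** One directional hypothesis is served by three tests, each with its own 0.05 threshold. The available text gives no order of testing, no division of alpha and no statement of which result decides. Section 8.1.3 calls only the immunologic correlative comparisons exploratory, so the CTL019 comparisons read as inferential. Any one of the three could be reported as statistically significant support for enhancement.

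The three sections also leave the endpoint and the population open. Under 8.1.2(2) the group may be too small for any test to reach 0.05. A reader following Section 1 could run PFS in everyone and obtain a p-value that 8.1.2(2) would not allow. At stake is a secondary efficacy claim. No stopping rule, sample size or success criterion depends on these tests.

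**Working it through.** **The plan's own figure.** Section 8.1.2 states 12 patients for 80% power in the response-rate test (5% versus 35%, one-sided 0.05). With rejection at 3 or more of 12, exact alpha is 0.0196 and power 0.849; 11 patients give 0.7999, so 12 reproduces. Objective (2) states no sample size, power or overall error rate.

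**Can the tests reach 0.05?** Take complete separation with no censoring. Sum observed minus expected events (O−E) and variances (V) over event times in the earlier-failing group.
- 2 versus 2: E = 2/4 + 1/3 = 0.8333; V = 0.25 + 0.2222 = 0.4722; O−E = 1.1667; chi-square = 1.3611/0.4722 = 2.88; p = 0.090.
- 3 versus 3: E = 0.5 + 0.4 + 0.25 = 1.15; V = 0.25 + 0.24 + 0.1875 = 0.6775; O−E = 1.85; chi-square = 3.4225/0.6775 = 5.05; p = 0.025.

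At least 3 double responders are therefore needed.

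**How many double responders?** The 35% rate is from 8.1.2(1). The share of enrolled patients who had responded to CTL019 is not given. Assume 50% (range 30% to 70%), independent of response to pembrolizumab.
- Expected: 12 × 0.35 × 0.5 = 2.1 (1.26 to 2.94).
- Chance of 3 or more, Binomial(12, 0.175): 1 − 0.099 − 0.253 − 0.295 = 0.352 (0.124 to 0.594).

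The preliminary data in Section 4.2.1 point lower. They show 6 non-responders with diffuse large B-cell lymphoma, 1 follicular responder who progressed, and 1 large-cell responder not in ongoing complete response. At most 2 of those 8 (25%) were prior responders, giving 12 × 0.35 × 0.25 = 1.05 expected. More responders may relapse with longer follow-up.

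**Error rate of the three tests.** For tests at an exact 5% level, three independent tests give 1 − 0.95³ = 14.3%, and 15% is the ceiling. These endpoints overlap, so the rate was simulated. Assumptions, none stated in the plan: exponential response duration with mean 12 months; PFS = time to response (mean 3 months) + response duration; EFS adds other events at 0 to 2 times the progression rate; 24 months' follow-up; no true difference; 40,000 runs per setting.

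| Patients per side | Single PFS test | Any of three (extra EFS events 0 to 2×) | In favour of pembrolizumab |
|---|---|---|---|
| 3 | 9.7–9.9% | 11.0–19.1% | 5.5–9.6% |
| 4 | 5.5–5.8% | 6.6–11.3% | 3.4–5.7% |
| 6 | 6.9–7.1% | 7.9–14.2% | 3.9–7.3% |
| 12 | 5.8–5.9% | 6.5–11.8% | 3.3–6.1% |
| 50 | 5.1–5.3% | 5.6–10.2% | 2.7–5.2% |

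Any-of-three divided by the mean single-test rate is 1.1 to 2.0 throughout. The remaining excess over 5%, largest at 3 per side, is failure of the chi-square approximation. In one variant with positive within-patient correlation (extra EFS events at 0.5×), any-of-three was 10.2% at 3 per side and 4.1% to 6.7% at 4 or more.

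**Unconditional rate.** The any-of-three rates, with extra EFS events at 0 to 1×, were weighted by the binomial chance of each group size:
- 50% prior responders (0.175 double responders): 3.3% to 5.4%.
- 80% (0.35 × 0.8 = 0.28): 6.0% to 9.9%.
- 100% (0.35): 7.0% to 11.6%.

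**PFS in all treated patients.** Section 5.1.1 admits only patients whose lymphoma was relapsed or refractory after CTL019/CTL119, so every CTL019/CTL119 PFS time is an observed failure. Pembrolizumab PFS can be censored. With 12 patients, the same exponential PFS on both sides, CTL019/CTL119 failure assumed to fall within 24 months and 24 months' follow-up, the log-rank test favoured pembrolizumab at p≤0.05 in about 13% to 14% of trials at a 12-month mean PFS, and 57% to 58% at 24 months. The result depends strongly on the assumed window.

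**The case against.** The strongest reply is that this is a 12-patient, single-arm trial with a safety primary objective, and that objective (2) is worded as a description. Formal alpha control would be out of proportion. That stands against an alpha split or a testing hierarchy. It does not explain why a descriptive objective carries a significance threshold and a directional hypothesis.

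A reader might infer that the false-positive rate for enhancement is two to three times 5%. The documents do not support this. Two or three independent tests would give 9.75% to 14.3%, but these endpoints are overlapping measures on the same few patients. A two-sided rejection against pembrolizumab is not a false claim of enhancement. At the central assumption the tests usually cannot be significant at all.

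A reader might also count six or more tests by adding the response-rate and prior-therapy comparisons. The plan gives neither a test nor a threshold, so they are undefined comparisons rather than extra chances at 0.05. Nor does Section 1 specify an all-patient analysis: it is a one-line summary, silent on population, and its PFS test may be one of the three in 8.1.2(2).

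Finally, a block of text between objective (2) and Section 8.1.3 is not in the copy available, so the absence of a deciding contrast is a statement about the available text.

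**Conclusion.** The concern holds as a defect of specification. Three p≤0.05 claims serve one hypothesis, none is named as deciding, and Sections 1, 3.2 and 8.1.2 disagree on endpoint and population. Given 3 or more double responders, the any-of-three rate is roughly 6% to 19% two-sided, about half of it favouring pembrolizumab; multiplicity contributes a factor of 1.1 to 2. At 35% response and 50% prior responders the unconditional rate is about 3% to 5.5%, so inflation is not the main argument. The main argument is that a significance label is attached to comparisons that either cannot reach it or cannot support it.

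The figures rest on the assumed EFS definition, endpoint overlap and prior-responder share. They also leave out selection: double responders too have relapsed after CTL019/CTL119 or they would not be enrolled, so restricting to them removes CTL019 non-responders but not the bias towards pembrolizumab. The conclusion does not depend on the exact rate.

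**What to change.** - In 8.1.2(2), delete "with $p \leq 0.05$ considered statistically significant". Label every comparison with CTL019/CTL119 (PFS, EFS, response duration, response rate) descriptive, reported as estimates with confidence intervals and no significance claim.
- Align Sections 1, 3.2 and 8.1.2 on the same endpoints and the same population.
- Define or delete the comparison with most recent prior therapy. Under exclusion 2 it is either CTL019/CTL119 itself or an earlier line that the plan does not name.
- Do not promote a PFS log-rank test in all treated patients to the deciding contrast. Eligibility requires failure of CTL019/CTL119, which favours pembrolizumab under no true difference.

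The cost is protocol and analysis-plan wording only, with no new patients or data. The downside is that none of these comparisons can then be called statistically significant. The response-rate test in 8.1.2(1) is unaffected.
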